## **6.2 Nonserious Adverse Events**

A *nonserious adverse event* is an AE not classified as serious.

### **6.2.1 Nonserious Adverse Event Collection and Reporting**

The collection of nonserious AE information should begin at initiation of study drug. Nonserious AE information should also be collected from the start of a placebo lead-in period or other observational period intended to establish a baseline status for the subjects.

Nonserious AEs should be followed to resolution or stabilization, or reported as SAEs if they become serious (see [Section 6.1.1](#)). Follow-up is also required for nonserious AEs that cause interruption or discontinuation of study drug and for those present at the end of study treatment as appropriate. All identified nonserious AEs must be recorded and described on the nonserious AE page of the CRF (paper or electronic).

Completion of supplemental CRFs may be requested for AEs and/or laboratory abnormalities that are reported/identified during the course of the study.

## **6.3 Laboratory Test Result Abnormalities**

The following laboratory test result abnormalities should be captured on the nonserious AE CRF page or SAE Report Form (electronic) as appropriate. Paper forms are only intended as a back-up option when the electronic system is not functioning.

- Any laboratory test result that is clinically significant or meets the definition of an SAE
- Any laboratory test result abnormality that required the subject to have study drug discontinued or interrupted
- Any laboratory test result abnormality that required the subject to receive specific corrective therapy

It is expected that wherever possible, the clinical rather than laboratory term would be used by the reporting investigator (eg, anemia versus low hemoglobin value).

#### **6.4 Pregnancy**

If, following initiation of the study drug, it is subsequently discovered that a study subject is pregnant or may have been pregnant at the time of study exposure, including during at least 5 half lives after product administration, the investigator must immediately notify the Sponsor or designee of this event and complete and forward a Pregnancy Surveillance Form to BMS Designee within 24 hours of awareness of the event and in accordance with SAE reporting procedures described in [Section 6.1.1](#).

If the investigator determines a possible favorable benefit/risk ratio that warrants continuation of study treatment, or re-initiation of study treatment, a discussion between the investigator and the BMS Medical Monitor/designee must occur. If, for whatever reason, the pregnancy has ended, confirmed by negative serum pregnancy test, treatment may be resumed (at least 3 weeks and not greater than 6 weeks after the pregnancy has ended), following approvals of participant /sponsor /IRB/EC, as applicable.

Follow-up information regarding the course of the pregnancy, including perinatal and neonatal outcome and, where applicable, offspring information must be reported on the Pregnancy Surveillance Form.

Any pregnancy that occurs in a female partner of a male study participant should be reported to Sponsor or designee. In order for BMS to collect any pregnancy surveillance information from the female partner, the female partner must sign an informed consent form for disclosure of this information. Information on this pregnancy will be collected on the Pregnancy Surveillance Form.

#### **6.5 Overdose**

An overdose is defined as the accidental or intentional administration of any dose of a product that is considered both excessive and medically important. All occurrences of overdose must be reported as an SAE (see Section 6.1.1 for reporting details.).

#### **6.6 Potential Drug Induced Liver Injury (DILI)**

Wherever possible, timely confirmation of initial liver-related laboratory abnormalities should occur prior to the reporting of a potential DILI event. All occurrences of potential DILIs, meeting the defined criteria, must be reported as SAEs (see Section 6.1.1 for reporting details).

Potential drug induced liver injury is defined as:

1. AT (ALT or AST) elevation > 3 times upper limit of normal (ULN)  
AND
2. Total bilirubin > 2 times ULN, without initial findings of cholestasis (elevated serum alkaline phosphatase),  
AND
3. No other immediately apparent possible causes of AT elevation and hyperbilirubinemia, including, but not limited to, viral hepatitis, pre-existing chronic or acute liver disease, or the administration of other drug(s) known to be hepatotoxic.

## 6.7 Other Safety Considerations

Any significant worsening noted during interim or final physical examinations, electrocardiogram, x-ray filming, any other potential safety assessment required or not required by protocol should also be recorded as a nonserious or serious AE, as appropriate, and reported accordingly.

### 6.7.1 Adverse Events of Interest

Definition of immune-mediated adverse events (IMAEs)

Immune-mediated AEs are specific events (that include pneumonitis, diarrhea/colitis, hepatitis, nephritis/renal dysfunction, rash, and endocrine (adrenal insufficiency, hypothyroidism/thyroiditis, hyperthyroidism, diabetes mellitus, and hypophysitis) for which subjects received immunosuppressive medication for treatment of the event, with the exception of endocrine events (hypothyroidism/thyroiditis, hyperthyroidism, hypophysitis, diabetes mellitus, adrenal insufficiency), which are included regardless of treatment since these events are often managed without immunosuppression.

IMAEs include events, regardless of causality, occurring within 100 days of the last dose. This list is subject to change based on Health Authority feedback or change of Medical Dictionary for Regulatory Activities (MedDRA) version. The final list used will be described in the clinical study report (CSR).

Table 6.7.1-1 below provides a summary of the IMAEs category and their respective preferred terms (PTs). This list is subject to change based on Health Authority feedback or change of MedDRA version. The final list used will be described in the CSR.

**Table 6.7.1-1: Preferred Terms Included in Analysis of IMAEs to Support Warnings and Precautions**

IMAE Category	PTs included under IMAE Category
Pneumonitis	Pneumonitis, Interstitial lung disease
Diarrhea/Colitis	Diarrhea, Colitis, Enterocolitis

**Table 6.7.1-1: Preferred Terms Included in Analysis of IMAEs to Support Warnings and Precautions**

IMAE Category	PTs included under IMAE Category
Hepatitis	Hepatotoxicity, Hepatitis, Hepatitis acute, Autoimmune hepatitis, AST increased, ALT increased, Bilirubin increased, ALP increased
Adrenal insufficiency	Adrenal insufficiency
Hypothyroidism/Thyroiditis	Hypothyroidism, Thyroiditis Thyroiditis acute (collapsed with thyroiditis for frequency), Autoimmune thyroiditis (collapsed with thyroiditis for frequency)
Hyperthyroidism	Hyperthyroidism
Hypophysitis	Hypophysitis
Diabetes mellitus	Diabetes mellitus, Diabetic ketoacidosis
Nephritis and renal dysfunction	Nephritis, Nephritis allergic, Tubulointerstitial nephritis, Acute renal failure, Renal failure, Increased creatinine
Rash	Rash, Rash maculopapular

## **7. DATA MONITORING COMMITTEE AND OTHER EXTERNAL COMMITTEES**

A Data Monitoring Committee (DMC) will be utilized to provide general oversight and safety considerations for this study. The DMC will provide advice to the Sponsor regarding actions the committee deems necessary for the continuing protection of subjects enrolled in this study. The DMC will be charged with assessing such actions in light of an acceptable risk/benefit profile for nivolumab in combination with placebo, and nivolumab in combination with ipilimumab. The DMC will act in an advisory capacity to BMS and will monitor subject safety data for the study approximately every 6 months for the duration of the trial.

The DMC will be advisory to the clinical study leadership team. The clinical study leadership will have responsibility for overall conduct of the study including managing the communication of study data. The group will be responsible for promptly reviewing the DMC recommendations, for providing guidance regarding the continuation or termination of the study, and for determining whether amendments to the protocol or changes to the study conduct are required.

Details of the DMC responsibilities and procedures will be specified in the DMC charter.

When required, adjudicated events will be submitted to the DMC and Health Authorities for review on a specified timeframe in accordance with the adjudication documentation.

## 8. STATISTICAL CONSIDERATIONS

### 8.1 Sample Size Determination

The primary objective is to compare the ORR of nivolumab in combination with ipilimumab vs nivolumab in combination with ipilimumab placebo, as determined by BICR using Response Evaluation Criteria In Solid Tumors (RECIST 1.1) criteria in platinum refractory subjects with recurrent or metastatic SCCHN. The alpha level for the ORR is adjusted for one planned interim analysis using Lan-DeMets alpha spending function with O’Brien-Fleming boundaries. Given that the interim analysis for the primary endpoint is expected to be performed when 70% of platinum refractory subjects have reached 6 months follow up after randomization, the alpha level is expected to be 0.015 for the interim analysis and 0.045 for the final analysis.

Approximately 396 subjects (216 platinum refractory subjects and 180 platinum eligible subjects) will be randomized to either nivolumab plus ipilimumab or nivolumab in combination with ipilimumab placebo in a 2:1 ratio.

A sample size of 216 randomized platinum refractory subjects (144 and 72, respectively) will provide 84% power for testing the odds ratio of nivolumab plus ipilimumab over nivolumab in combination with placebo, with a 0.050 two-sided significance level, assuming ORR of 35% and 15% (odds ratio of 3.051) in the nivolumab plus ipilimumab and nivolumab in combination with ipilimumab placebo treatment group, respectively (odds ratio of proportions test using EAST v6).

The first secondary objective is to estimate the ORR of the treatment of nivolumab in combination with ipilimumab vs nivolumab in combination with ipilimumab placebo, as determined by BICR using RECIST 1.1 criteria for first-line treatment of recurrent or metastatic SCCHN in the platinum eligible setting.

Approximately 180 subjects (120 and 60, respectively) will be randomized in the platinum eligible subgroup. For a sample size of 120 subjects randomized to nivolumab plus ipilimumab, the maximum width of the exact two-sided 95% confidence interval (CI) is 18.6% when the ORR is expected to be in the 10% to 55% range. The table below summarizes the 95% exact CI when observed ORRs are between 10% and 55% respectively.

**Table 8.1-1: Observed ORR with Exact 95% CI in Platinum Eligible Subjects randomized to nivolumab plus ipilimumab (N=120)**

Observed ORR	95% Exact CI
10%	(5.3%, 16.8%)
20%	(13.3%, 28.3%)
30%	(22.0%, 39.0%)
40%	(31.2%, 49.3%)
50%	(40.7%, 59.3%)
55%	(45.7%, 64.1%)

About 60 subjects will be randomized to nivolumab plus ipilimumab placebo arm. The following table summarizes the 95% exact CI when observed ORRs are between 10% and 55%.

**Table 8.1-2: Observed ORR with Exact 95% CI in Platinum Eligible Subjects randomized to nivolumab plus ipilimumab placebo (N=60)**

Observed ORR	95% Exact CI
10%	(3.8%, 20.5%)
20%	(10.8%, 32.3%)
30%	(18.8%, 43.2%)
40%	(27.6%, 53.5%)
50%	(36.8%, 63.2%)
55%	(41.6%, 67.9%)

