**Statistical Considerations:**

**Sample Size:**

Approximately 396 subjects (approximately 216 platinum refractory subjects and approximately 180 platinum eligible subjects) will be randomized to either nivolumab in combination with ipilimumab or nivolumab in combination with ipilimumab placebo in a 2:1 ratio.

A sample size of 216 randomized platinum refractory subjects (144 and 72, respectively) will provide 84% power for testing the odds ratio of nivolumab in combination with ipilimumab or over nivolumab in combination with ipilimumab placebo, with a 0.050 two-sided significance level, assuming ORR of 35% and 15% (odds ratio of 3.051) in the nivolumab in combination with ipilimumab or and nivolumab in combination with ipilimumab placebo treatment groups respectively (odds ratio of proportions test using EAST v6).

Approximately 180 subjects (120 and 60, respectively) will be randomized in the platinum eligible subgroup. For a sample size of 120 subjects randomized to nivolumab plus ipilimumab, the maximum width of the exact two-sided 95% confidence interval (CI) is 18.6% when the ORR is expected to be in the 10% to 55% range. About 60 subjects will be randomized into nivolumab and ipilimumab placebo arm.

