**8.4.2.1 Method for primary endpoint**

The comparison of ORR between nivolumab in combination with ipilimumab vs nivolumab in combination with ipilimumab placebo in platinum refractory randomized subjects will be carried out using a two-sided Cochran Mantel Haenszel (CMH) test stratified by the stratification factors as recorded in the IVRS. The significance level will be adjusted for an interim analysis which will be performed when around 70% of platinum-refractory subjects have been followed for at least 6 months after randomization. Using Lan DeMets alpha spending function with O'Brien-Fleming boundaries, the significance level for this comparison will be determined by the fraction of subjects included in the interim analysis. If the analysis is performed when exactly 70% of platinum refractory subjects have reached 6 months follow up after randomization, the alpha level is 0.015 for the interim and 0.045 for the final. An associated odds ratio and corresponding CIs (98.5% CI for interim and 95.5% CI for final) will be calculated. ORR will be summarized by a binomial response rate and its corresponding two-sided exact CIs using Clopper-Pearson method for each treatment group. An estimate of the difference in ORRs and corresponding CIs will be calculated using CMH methodology and adjusted by the stratification factors as recorded in the IVRS. Summary statistics of TTR will be provided for each treatment group for subjects who achieve PR or CR. Duration of response (DOR) in each treatment group will be estimated using KM product-limit method for subjects who achieve PR or CR. Median values along with two-sided 95% CI will be calculated.

[REDACTED]

[REDACTED]

[REDACTED]

[REDACTED]

[REDACTED]

[REDACTED]

[REDACTED]

[REDACTED]

[REDACTED]

[REDACTED]

[REDACTED]

[REDACTED]

[REDACTED]

[REDACTED]

[REDACTED]

[REDACTED]

[REDACTED]

[REDACTED]

[REDACTED]

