## 5 SAMPLE SIZE AND POWER

The primary objective is to compare the ORR of nivolumab in combination with ipilimumab vs nivolumab in combination with ipilimumab placebo, as determined by BICR using Response Evaluation Criteria In Solid Tumors (RECIST 1.1) criteria in platinum refractory subjects with recurrent or metastatic SCCHN. The alpha level for the ORR is adjusted for one planned interim analysis using Lan-DeMets alpha spending function with O’Brien-Fleming boundaries, which will be determined by the fraction of subjects included in the interim analysis. Given that the interim analysis for the primary endpoint is expected to be performed when 70% of platinum refractory subjects have reached 6 months follow up after randomization, the alpha level is expected to be 0.015 for the interim analysis and 0.045 for the final analysis.

Approximately 396 subjects (216 platinum refractory subjects and 180 platinum eligible subjects) will be randomized to either nivolumab plus ipilimumab or nivolumab in combination with ipilimumab placebo in a 2:1 ratio.

A sample size of 216 randomized platinum refractory subjects (144 and 72 respectively) will provide 84% power for testing the odds ratio of nivolumab plus ipilimumab over Nivolumab in combination with placebo, with a 0.050 two-sided significance level, assuming ORR of 35% and 15% (odds ratio of 3.051) in the nivolumab plus ipilimumab and nivolumab in combination with ipilimumab placebo treatment group respectively (odds ratio of proportions test using EAST v6).

Only the primary endpoint will be tested, none of the secondary endpoints.

The first secondary objective is to estimate the ORR of the treatment of nivolumab in combination with ipilimumab vs nivolumab in combination with ipilimumab placebo, as determined by BICR using RECIST 1.1 criteria for first line treatment of recurrent or metastatic SCCHN in the platinum eligible setting.

Approximately 180 subjects (120 and 60 respectively) will be randomized in the platinum eligible subgroup. For a sample size of 120 subjects randomized to nivolumab plus ipilimumab, the maximum width of the exact two-sided 95% confidence interval (CI) is 18.6% when the ORR is expected to be in the 10% to 55% range. The table below summarizes the 95% exact CI when observed ORRs are between 10% and 55% respectively.

Table 5-1: Observed ORR with Exact 95% CI in Platinum Eligible Subjects randomized to nivolumab plus ipilimumab (N=120).

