#### 7.5.1.1 Primary Analysis of ORR

The comparison of ORR between nivolumab in combination with ipilimumab vs nivolumab in combination with ipilimumab placebo in platinum refractory randomized subjects will be carried out using a two-sided Cochran-Mantel-Haenszel (CMH) test stratified by the stratification factors PD-L1 status (expressing vs non-expressing/non-evaluable/indeterminate) and HPV p-16 status (oropharyngeal HPV p16 positive (including unknown primary with HPV p16 positive) vs oropharyngeal HPV p16 negative or nonoropharyngeal) as recorded in the IVRS. The significance level will be adjusted for an interim analysis which will be performed when around 70% of platinum-refractory subjects have been followed for at least 6 months after randomization. Using Lan-DeMets alpha spending function with O'Brien-Fleming boundaries, the significance level for this comparison will be determined by the fraction of subjects included in the interim analysis. If the analysis is performed when exactly 70% of platinum refractory subjects have reached 6 months follow up after randomization, the alpha level is 0.015 for the interim and 0.045 for the final. An associated odds ratio (nivolumab/ipilimumab vs. nivolumab/ipilimumab placebo) and corresponding CI will be calculated. ORR will be summarized by a binomial response rate and its corresponding two-sided exact CI using Clopper-Pearson method for each treatment group. An estimate of the difference in ORRs between arms (nivolumab/ipilimumab vs. nivolumab/ipilimumab placebo) and corresponding CI will be calculated using Cochran-Mantel-Haenszel (CMH) methodology and adjusted by the stratification factors as recorded in the IVRS.

The formula is

$$\hat{\theta} = \frac{\sum_i w_i \hat{\theta}_i}{\sum_i w_i} \sim N \left[ \theta, \frac{\sum_i w_i^2 \left[ \frac{p_{ix}(1-p_{ix})}{n_{ix}-1} + \frac{p_{iy}(1-p_{iy})}{n_{iy}-1} \right]}{\left( \sum_i w_i \right)^2} \right]$$

where  $\hat{\theta} = p_{ix} - p_{iy}$  is the difference in rates in the *i*th stratum,  $w_i = \frac{n_{ix}n_{iy}}{n_{ix} + n_{iy}}$ , and  $n_{ix}$  and  $n_{iy}$  are the number of subjects randomized to treatments x and y, respectively, in the *i*th stratum.

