#### **7.5.6 Interim Analysis**

One interim analysis will be performed when around 70% of platinum-refractory subjects have been followed for at least 6 months after randomization. The comparison of ORR between nivolumab in combination with ipilimumab vs nivolumab in combination with ipilimumab placebo in platinum refractory randomized subjects will be carried out using a two-sided Cochran-Mantel-Haenszel (CMH) test stratified by the stratification factors as recorded in the IVRS. Using Lan-

DeMets alpha spending function with O'Brien-Fleming boundaries, the significance level for this comparison will be determined by the fraction of subjects included in the interim analysis. If the analysis is performed when exactly 70% of platinum refractory subjects have reached 6 months follow up after randomization, the alpha level is 0.015. Point estimate of ORR, and its corresponding two-sided 98.5% exact CI will be provided for each treatment group. The difference in ORRs between the two treatment groups and its corresponding 98.5% CI will be calculated using CMH methodology and adjusted by the stratification factors as recorded in the IVRS.

The following sensitivity analyses may be conducted using the primary definition of ORR in platinum-refractory subjects:

- If one stratification variable at IVRS and at baseline (CRF and clinical database) disagrees for at least 10% of the randomized subjects, similar analysis of ORR will be performed using the strata as determined at baseline.
- ORR per BICR for subjects with no relevant deviation. This analysis will be conducted only if there are more than 5% subjects with relevant protocol deviations.

The DOR distribution will be estimated using Kaplan-Meier technique. Median survival time along with 95% CI will be provided for each treatment group.

The PFS and OS distribution will also be estimated using Kaplan-Meier technique. Median survival time along with 95% CI will be provided for each treatment group. The hazard ratio and the 95% confidence interval will be estimated in a stratified Cox proportional hazards model using the randomized arm as a single covariate, stratified by PD-L1 status and HPV p-16 status.

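### Does the stated 84% power need correcting because it comes from an odds-ratio formula rather than from the planned stratified CMH test?

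*Protocol*

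**What the plan says.** The power statement appears three times with the same inputs. Protocol 8.1 has "will provide 84% power for testing the odds ratio of nivolumab plus ipilimumab over nivolumab in combination with placebo", SAP section 5 has "will provide 84% power for testing the odds ratio of nivolumab plus ipilimumab over Nivolumab in combination with placebo", and the synopsis has "will provide 84% power for testing the odds ratio of nivolumab in combination with ipilimumab or over nivolumab in combination with ipilimumab placebo". Each assumes response rates of 35% and 15% (odds ratio 3.051), 144 and 72 subjects, and a two-sided 0.050 level. Each names the method: "odds ratio of proportions test using EAST v6".

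The analysis is specified separately. Under Protocol 8.4.2.1 the comparison "will be carried out using a two-sided Cochran Mantel Haenszel (CMH) test stratified by the stratification factors as recorded in the IVRS"; SAP 7.5.1.1 names PD-L1 status and HPV p-16 status as the factors, which makes four strata within the platinum refractory subgroup. SAP 7.5.6 states "One interim analysis will be performed when around 70% of platinum-refractory subjects have been followed for at least 6 months after randomization". For an interim at exactly 70%, SAP 7.5.1.1 says "the alpha level is 0.015 for the interim and 0.045 for the final". SAP section 5 adds: "Only the primary endpoint will be tested, none of the secondary endpoints".

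**The concern.** The test behind the power figure is not the test that will be run. Power is quoted for an odds-ratio comparison at 0.050, whereas the analysis is a stratified CMH test at 0.015 and then 0.045. A reader cannot tell from the text whether 84% allows for the interim look.

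Recalculating for the CMH test gives a figure about five points higher, which looks like an arithmetic mistake. Because this is the only endpoint to be tested, its power is the one power figure in the plan that matters. A mistake in the other direction would have meant an underpowered trial. Even in this direction, the implied type II error would be about 11% rather than 16%.

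**Working it through.** **Inputs** (Protocol 8.1): p1 = 0.35, n1 = 144; p0 = 0.15, n0 = 72; two-sided 0.050 overall; 0.015 and 0.045 at the two looks; interim at 70%, about 151 of 216 subjects.

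**Step 1: reproduce the 84%.** Large-sample log odds-ratio formula:

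- Odds ratio = (0.35 × 0.85) / (0.65 × 0.15) = 3.051, as stated; its log is 1.1156.
- Variance = 1/(144 × 0.35 × 0.65) + 1/(72 × 0.15 × 0.85) = 1/32.76 + 1/9.18 = 0.1395; SE = 0.3734.
- Standardised effect = 1.1156 / 0.3734 = 2.987.
- Single look at 0.05: Φ(2.987 − 1.960) = 84.8%.
- Single look at 0.045: Φ(2.987 − 2.005) = 83.7%.
- Two looks at 0.015 and 0.045, correlation √0.70: 84.2%.

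The two-look value is the closest match, since 84.8% would round to 85%. The stated figure may therefore already include the interim, with 0.050 as the overall level. The documents do not settle this, and the log scale is itself inferred from the match.

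**Step 2: check the boundaries.** The Lan-DeMets O'Brien-Fleming function at 0.70 gives 0.0148 and 0.0455, consistent with 0.015 and 0.045.

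**Step 3: exact power without strata.** Enumerating all 145 × 73 outcomes at 35% and 15%:

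| Test | 0.05 | 0.045 |
|---|---|---|
| Wald log odds ratio | 89.3% | 88.6% |
| Mantel-Haenszel | 89.9% | 88.7% |
| Mantel-Haenszel, 0.5 correction | 86.5% | 85.1% |

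The gap is not mainly between the odds-ratio test and the CMH test, which agree closely. It lies between the large-sample formula and exact power: 84.8% against 89.3% for the same Wald test at 0.05. Only 72 × 0.15 = 10.8 control responders are expected. With so few, the estimated standard error rises and falls with the estimated log odds ratio, so the test statistic varies less than the formula assumes and falls below the critical value less often.

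**Step 4: the planned test.** Simulation of the two-look stratified CMH test at 0.015 and 0.045, with looks at 151 and 216 subjects. The documents give no strata prevalences or prognostic effects, so these are assumptions:

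| Assumed strata | No correction | 0.5 correction |
|---|---|---|
| Four strata, equal response rates | 89.0–89.3% | 85.1–85.7% |
| Moderately prognostic | 89.7% | 86.2% |
| Strongly prognostic | 91.5% | 87.9% |

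Without the correction, simulated type I error is 4.8% to 4.9%. If interim response rates are 10% to 20% lower in relative terms, uncorrected power stays at 89.1% to 89.2%.

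**Step 5: scale.** Exact Mantel-Haenszel power at 0.045, uncorrected, falls from 88.7% to 84.5% if the control rate is 16% rather than 15%, and to 83.7% if the combination rate is 33.5% rather than 35%.

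**The case for a change.** The best argument for a change is that a power statement should describe the test that will be used. Here it concerns the only tested endpoint, it rests on an approximation that understates even its own test by 4.5 points (89.3 − 84.8), and the remedy is a sentence in three places. Power also affects how a non-significant result is read, and a type II error of 11% differs from 16%.

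Part of this stands. The sizing method and the analysis method do differ. Whether 84% includes the interim is unstated, and so is any continuity correction. A plan written afresh could reasonably give the CMH figure alongside.

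The rest carries less weight. The sentence attributes 84% to an odds-ratio method and does not claim it for the CMH test, so nothing in it is false. The proposed 89% is conditional: it needs assumed strata and no continuity correction, and the fair range is about 85% to 91.5%. Replacing a reproducible figure with a simulated one would mean writing into the plan choices that it has not made. A non-significant result would be read from the confidence intervals for the odds ratio and the rate difference, which are already planned at levels matched to the two looks, rather than from planning power. As for the continuity correction, the plan names none, so the natural reading is the uncorrected test. On either reading, power is above the stated 84%.

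**Conclusion.** No change to the plan. The 84% is a disclosed, reproducible planning figure (84.8% at one look, 84.2% at two), and it errs on the safe side. At the plan's own 35% and 15%, the two-look stratified CMH test has roughly 89% to 91.5% power uncorrected and 85% to 88% corrected, so the trial has at least the power it states. A difference of about five points is no larger than the effect of moving the control rate by one percentage point, so quoting the higher figure would not make the design better understood in any useful way. Following the plan as written gives a valid test with type I error just under 5%.

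This conclusion rests on the assumed strata mixes, a common odds ratio across strata in the prognostic scenarios, and similar treatment effects at both looks. The inference that the software used the log odds-ratio scale explains where 84% came from; it is not needed for the conclusion that the figure is conservative.
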